APPENDIX B: PK AND ATA SAMPLING TIME POINTS (Q3WK LV DOSING; PARTS A AND B)

_	Study							Pembrolizumab
Cycle ^C	Day	Time	Window	Relative Time	LV PK	Pembrolizumab PK	LV ATA	ATA
Cycle 1	Day 1	Predose of LV	Within 8 hrs	START of LV infusion	X	X	X	X
		End of LV infusion	Within 30 min	END of LV infusion	X			
		End of pembrolizum ab infusion	Within 30 min	END of pembrolizumab infusion		Х		
	Day 3 ^B	48 hrs	Day 3-4	START of LV infusion	X	X		
	Day 5 ^A	96 hrs	Day 4-7	START of LV infusion	X	Х		
	Day 8	168 hrs	±48 hrs	START of LV infusion	X	X		
	Day 15	336 hrs	±48 hrs	START of LV infusion	X	X		
Cycles 2 and 4	Day 1	Predose of LV	Within 8 hrs	START of LV infusion	X	X	X	X
		End of LV infusion	Within 30 min	END of LV infusion	X			
		End of pembrolizum ab infusion	Within 30 min	END of pembrolizumab infusion		Х		
Cycles 3, 5, and every 5 cycles thereafter (e.g., Cycles 10, 15)	Day 1	Predose of LV infusion	Within 8 hrs	START of LV infusion	Х	х	Х	х
EOT					X	X	X	X

A Day 5 assessments to be performed for patients in Part A only.

B Day 3 assessments (Part B Cycle 1 only) required for US patients, optional for EX-US patients. Requires separate informed consent for EX-US patients.

Biomarker assessments will only be collected during Cycle 1 as of protocol Amendment 11.

APPENDIX C: SCHEDULE OF EVENTS (PARTS C AND D)

						21-day Cycle			
		Baseline/S	creening	Enrollment	Dl	D8	D15	EOT	Follow-up
Visit Window	,	D-28 to 1	D-7 to 1	D-7 to 1	See footnotes for window	See footnotes for window	See footnotes for window	30-37 days post last dose	Every 6 weeks ±1 week ^{B,V}
Informed consent		X	2 / 101	2 / 10 1	***************************************	***************************************	TI ALLEGO III	and about	and treat
	Inclusion/exclusion	X		1					
	Medical history	X		1					
	Physical Exam		X	1	XAQ			X	X
	Height (baseline only) and Weight		X	1	X ^{A,Q}				
	Vital signs ^C		X	d to	X	X	X^U		
	Brain CT or MRI	X		흹					
	Initiate collection of archived tumor specimen (if available) ^{N,V}	x		Eligibility documentation submitted to sponsor prior to study start					
	Freshly obtained biopsy ^{D,M,T} (see also Appendix E)	x		nentati					
	ECG	X		8 2					
Safety	Pregnancy test (performed locally) (patients of childbearing potential only)		XE	ity do	XE			X	
Assessments	ECOG performance status		X	漫图	$X^{A,P}$			X	
1	Hepatitis B and C screening ^Q	X		.					
1	CBC with differential ^{M,Q}		X	-	X _{AQ}	X	X_{Ω}	X	
1	PT/PTT/aPTT/INRQ	X							
	HbAlc ^{G,Q}	X						X	
	Fasting blood glucose ^{F,Q}	X		1					
	Serum chemistry panel ^{M,Q}		X		XAGQ	$X^{G,R}$	$X^{GR,S}$	X	
	Thyroid function tests ^{H,Q}	x			(e.g.,	ch odd-numbered cycle w Day 1 of Cycles 1, 3, 5,	7, etc)		
	Concomitant medications & AEs	study protoc	lect any related procedure in from the tri- termination	s that result in al or study	Collect from Day 1 (pr	redose) through 30 days (through EOT visit, wh	(AEs) or 90 days (SAEs) ichever is later ^{BI}	post last dose or	Χ'n
Treatment ^K	LV ^{KO,P}				X	X	X ^s		
Treatment.	Pembrolizumab				X				
	Samples for PK							_	
PK/ATA	Samples for ATA				Cycle 1 Only: See	e PK/ATA/Biomarker Ta	ibles (Appendix D and A	ppendix E)	
	Blood sample for biomarker analysis								
Response	CT or MRI of chest, abdomen, pelvis (and neck if clinically indicated) ⁵	x			Assessments to be performed every 6 weeks (±3 days) for the first 12 months and every 12 weeks (±7 days) thereafter, regardless of dose delays (see Section 7.2)			Χ ^N	X_1
	Subsequent anticancer therapy status (may be conducted with in-clinic visit or via phone calls)								х

Survival status (may be conducted with in-				v
clinic visit or via phone calls)				^

- A For Cycle 1 only, if baseline visit activities occur within 2 days prior to Day 1, these assessments do not need to be repeated.
- B For patients who discontinue study treatment in the absence of disease progression, perform every 6 weeks (±1 week) until progression or initiation of a new anticancer therapy. After 1 year on study, reduce frequency to every 12 weeks (±1 weeks). All patients, including those with progressive disease, will be followed for survival until completion of the safety follow-up period, death, or study closure, whichever occurs first unless stated otherwise.
- Vital signs include respiratory rate, pulse rate, and systolic and diastolic blood pressure while patient is in a seated position, pulse oximetry, and temperature. Obtain within 60 minutes prior to LV infusion, within 60 minutes prior to pembrolizumab infusion (Day 1 only), and within 2 hours of ending each infusion, and during infusion/s as clinically indicated.
- D If archived tumor specimen is not collected and for patients with accessible tumors only. Core needle or excisional biopsy is preferred. If neither is possible, discuss with sponsor whether biopsy obtained via alternative methods may be appropriate.
- E Pregnancy test must be performed within 3 days prior to each Day 1 study drug dose.
- F If HbAlc or fasting blood glucose is elevated during screening, a repeat HbAlc or fasting blood glucose must be obtained.
- G Blood glucose sample should be obtained before administration of study drugs or any glucose-containing fluid. Hold dose if blood glucose level is >250 mg/dL or >13.9 mmol/L, testing may be repeated on same day of dosing. If HbAlc or fasting glucose are elevated (HbAlc ≥6.5%, fasting glucose ≥126 mg/dL or ≥7.0 mmol/L) upon repeat testing, patient should receive glucose management prior to or within one week of starting study treatment.
- H Thyroid function tests include TSH, T3 or free T3, and free T4.
- I To be collected if serious and considered to be study treatment-related.
- J For patients who discontinue study treatment in the absence of disease progression, perform every 6 weeks (±1 week) during the first year, then reduce frequency per institution's standard of care until progression or initiation of a new anticancer therapy unless otherwise stated.
- K The maximum dose is 200 mg per infusion.
- L Timing of response assessments should be calculated from Cycle 1 Day 1.
- M Refer to the laboratory manual for information on collection, processing, storage, and shipment of sample.
- N Not required if conducted within 4 weeks prior to EOT.
- O At least 7 days must elapse between administrations of LV. Hold dose if dosing criteria outline in Section 5.2.3.5 are not met.
- P For Cycle 2 and beyond, may be performed up to 2 days prior to Day 1.
- Q Laboratory assessments are to be performed locally and results are to be submitted to the central laboratory (with the exception of pregnancy testing); detailed in Section 7.5.3.
- R Cycles 1 and 2 only.
- S Part C only.
- T In Part D only, archival or freshly obtained tumor tissue will be used to determine eligibility based on PD-L1 CPS<10 status as determined locally by a PD-L1 IHC assay using the 22C3 clone.
- U Cycles 1 and 2 only for Part D and every cycle for Part C.
- V Follow-up will occur every 6 weeks (±1 weeks) 30 days post last treatment for patients on LV only and 90 days for those on pembrolizumab.

APPENDIX D: PK AND ATA SAMPLING TIME POINTS (PARTS C AND D)

Cycle	Study Day	Time ^C	Window	Relative Time	LV PK	Pembrolizumab PK	LV ATA	Pembrolizumab ATA
Cycle 1	Day 1	Predose of LV	Within 8 hrs	START of LV infusion	X	X	X	X
		End of LV infusion	Within 30 min	END of LV infusion	Х			
		End of pembrolizumab infusion	Within 30 min	END of pembrolizumab infusion		x		
	Day 3 ^A	48 hrs	Day 3-4	START of Day 1 LV infusion	Х			
	Day 8	Pre-dose of LV	Within 8 hrs	START of LV infusion	Х			
		End of LV infusion	Within 30 min	END of LV infusion	X			
	Day 15 ^B	Pre-dose of LV	Within 8 hrs	START of LV infusion	X			
		End of LV infusion	Within 30 min	END of LV infusion	X			
Cycles 2 and 4	Day 1	Predose of LV	Within 8 hrs	START of LV infusion	X	X	X	X
		End of LV infusion	Within 30 min	END of LV infusion	X			
Cycles 3, 5, and every 5 cycles thereafter (e.g., Cycles 10, 15)	Day 1	Predose of LV infusion	Within 8 hrs	START of LV infusion	Х	х	х	х
EOT				nts. Requires separate inform	Х	X	X	X

A Day 3 assessments required for US patients, optional for EX-US patients. Requires separate informed consent for EX-US patients

B Part C only.

C Biomarker assessments will only be collected during Cycle 1 as of protocol Amendment 11.

APPENDIX E: BIOMARKER SAMPLING TIME POINTS

Table 11: Biomarker sampling time points - Parts A and B*

Cycle	Study Day	Time ^C	Window	Relative Time	Cytokines	cfDNA	Exosomes	Immune subsets	TCRβ Cell Pellet	Fresh Biopsy
		N/A								
Screening	Day -28 to -1	N/A	N/A	N/A						X
	Day 1	Predose	Within 8 hr	START of infusion	х	Х	X	Х	X	
Cycle 1	Day 5	_	Day 4-7	START of infusion						X ^A
	Day 15	336 h	±24 hr	START of infusion						X ^A
Cycles 2, 3	Day 1	Predose	Within 8 hr	START of infusion	Х	Х	Х	Х	Х	·
EOT					X	X	X	X	X	XB

Biomarker sampling time points - Parts C and D* Table 12:

Cycle ^B	Study Day	Time	Window	Relative Time	Cytokines	cfDNA	TCRβ Cell Pellet	Fresh Biopsy
		N/A						
Screening	Day -28 to -1	N/A	N/A	N/A				X ^A
Cycle 1, 2, and 4	Day 1	Predose	Within 8 hr	START of infusion	X	X	x	
EOT					X	X	X	

^{*}If additional tests, including but not limited to tumor marker assessments, are performed as part of standard of care, please submit those results.

A Fresh tumor biopsy required if archival tissue is not available.

^{*}If additional tests, including but not limited to tumor marker assessments, are performed as part of standard of care, please submit those results.

A Patients in Part A with accessible tumors are required to have a biopsy between Days 15 and 21 of Cycle 1.

Optional biopsy; requires separate informed consent.

Biomarker assessments will only be collected during Cycle 1 as of protocol amendment 11.

B Biomarker assessments will only be collected during Cycle 1 as of protocol amendment 11.

APPENDIX F: PERFORMANCE STATUS SCALES CONVERSION

APPENDIX G: GUIDANCE ON CONTRACEPTION

For the purposes of this guidance, complete abstinence, if consistent with the subject's preferred lifestyle, is an acceptable form of contraception. Complete abstinence is defined as abstinence starting from the time of informed consent and continuing throughout the study and until the end of the safety follow-up period.

Acceptable methods for highly effective birth control (preventing conception)

Subjects who are of childbearing potential^a or whose partners are of childbearing potential^a and who are sexually active in a way that could lead to pregnancy may choose any TWO of the following methods:

Intrauterine device with failure rate <1%

Tubal ligation

Vasectomy (at least 90 days from the date of surgery with a semen analysis documenting azoospermia)

Barrier method/s (male or female condom with or without spermicide, cervical cap with or without spermicide, diaphragm with or without spermicide)

A person of childbearing potential is defined as anyone born female who has experienced menarche and who has not undergone surgical sterilization (e.g., hysterectomy, bilateral salpingectomy, bilateral oophorectomy) or has not completed menopause. Menopause is defined clinically as 12 months of amenorrhea in a person born female over age 45 in the absence of other biological, physiological, or pharmacological causes.

Acceptable methods for preventing secondary exposure to seminal fluid

Subjects born male and who are sexually active with a pregnant or breastfeeding person, must use the contraceptives in Option 1 or 2:

Option 1: Male condom (with or without spermicide) and cervical cap

Option 2: Male condom (with or without spermicide) and diaphragm

Unacceptable methods of contraception

Periodic abstinence

No method

Withdrawal

Rhythm

Spermicide only

Progestin-only pills

Concomitant use of female and male condoms

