4. STUDY POPULATION

Patients must meet all of the enrollment criteria to be eligible for this study. Eligibility criteria may not be waived by the investigator and are subject to review in the event of a good clinical practice audit and/or health regulatory authority inspection.

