recent/fresh tissue if it was collected after completion of the patient's most recent cytotoxic therapy. If neither is available, please discuss with medical monitor.

- The following baseline laboratory data:
 - absolute neutrophil count ≥1,500/µL
 - platelet count ≥100,000/µL
 - hemoglobin ≥8.0 g/dL
 - serum bilirubin ≤1.5x upper limit of normal (ULN) or ≤3x ULN for patients with Gilbert's disease
 - serum creatinine ≤1.5x ULN OR glomerular filtration rate (GFR) ≥60 mL/min/1.73 m² for patient with creatinine levels >1.5x institutional ULN. GFR calculation is found in Appendix N.
 - Alanine aminotransferase (ALT) and aspartate aminotransferase (AST) ≤1.5x ULN or ≤3x ULN if liver metastases are present
 - International normalized ratio (INR) or prothrombin time (PT) ≤1.5x ULN unless subject is receiving anticoagulant therapy as long as PT or partial thromboplastin time (PTT) is within therapeutic range of intended use of anticoagulants
 - Activated partial thromboplastin time (aPTT) ≤1.5x ULN unless subject is receiving anticoagulant therapy as long as PT or PTT is within therapeutic range of intended use of anticoagulants
- For patients of childbearing potential as defined in Section 4.3, the following stipulations apply:
 - a. Must have a negative serum or urine pregnancy test (minimum sensitivity 25 mIU/mL or equivalent units of beta human chorionic gonadotropin [β-hCG]) result within 3 days prior to the first dose of LV/pembrolizumab. Patients with false positive results and documented verification that the patient is not pregnant are eligible for participation.
 - b. Must agree not to try to become pregnant from the time of enrollment until at least 6 months after the final dose of study drug. If heterosexually active, must consistently use 2 highly effective methods of birth control (as defined in Appendix G) during this time period.
 - c. Must agree not to breastfeed or donate ova, starting at time of informed consent and continuing through 6 months after the final dose of study drug administration.
- 10. Male patients under the following conditions:
 - a. Must agree not to donate sperm starting at time of informed consent and continuing throughout the study period and for at least 6 months after the final study drug administration.

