 - b. If heterosexually active with non-pregnant, pregnant, or breastfeeding partner, must consistently use 2 highly effective methods of birth control (as defined in Appendix G) starting at time of informed consent and continuing throughout the study and for at least 6 months after the final dose of study drug administration.

Amendment 11: 19-Oct-2023

Page 39 of 152

11. Patient must provide written informed consent if they are able to. If a patient is unable to provide written informed consent, then written informed consent can be provided by a legally authorized representative (LAR) in accordance with local legal requirements.

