- 23. Active autoimmune disease that has required systemic treatment in past 2 years (i.e., with use of disease modifying agents, corticosteroids, or immunosuppressive drugs). Replacement therapy (e.g., thyroxine, insulin, or physiologic corticosteroid replacement therapy for adrenal or pituitary insufficiency, etc.) is not considered a form of systemic treatment.
- History of interstitial lung disease.
- Current pneumonitis, or history of (non-infectious, including radiation induced) pneumonitis that required steroids.
- 26. Has a diagnosis of immunodeficiency or is receiving chronic systemic steroid therapy (in doses exceeding 10 mg daily of prednisone equivalent) or any other form of immunosuppressive therapy within 7 days prior to the first dose of study treatment. The use of corticosteroids for physiological replacement may be approved after consultation with the sponsor.
- 27. Patients who are breastfeeding, pregnant, or planning to become pregnant from time of informed consent until 6 months after final dose of study drug administration.
- Known hypersensitivity to any excipient contained in the drug formulation of LV or pembrolizumab.
- 29. Has received transfusion of blood products (including platelets or red blood cells) or administration of colony stimulating factors (including G-CSF, granulocyte macrophage colony-stimulating factor [GM-CSF], or recombinant erythropoietin) within 4 weeks prior to study Day 1.
- 30. Other serious underlying medical condition that, in the opinion of the investigator, would impair the ability to receive or tolerate the planned treatment and follow-up; any psychiatric or substance abuse disorders that would interfere with the participant's ability to cooperate with the requirements of the trial.
- Has received a live vaccine within 30 days of planned start of study therapy.
 - a. Note: seasonal influenza vaccines for injection are generally inactivated flu vaccines and are allowed; however intranasal influenza vaccines (e.g., Flu-Mist) are live attenuated vaccines and are not allowed.
- 32. Has not recovered (e.g., to ≤ Grade 1 or to baseline) from AEs due to a previously administered therapy.
- Has had an allogenic tissue/solid organ transplant.

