6.6. Follow-up

Patients who discontinue study treatment in the absence of disease progression will remain on the study for follow-up until withdrawal of consent, initiation of a new anticancer therapy, death, or study closure, whichever occurs first. The first follow-up visit will occur 6 weeks (±1 week) from the most recent prior radiographic response evaluation. Subsequent follow-up visits will be scheduled for 6 weeks (±1 week) from the previous follow-up visit. After 1 year on study, the frequency of follow-up visits will be reduced to every 12 weeks (±1 week).

The following assessments will be conducted at follow-up visits until progression or initiation of a new anticancer treatment through the end of the safety follow-up period:

- Physical examination (see Section 7.5.4)
- CT of chest, abdomen, and pelvis (and neck if clinically indicated) (MRI may also be
 acceptable; see Section 7.1); after a year of follow-up, reduce frequency to institution's
 standard of care until progression or initiation of a new anticancer therapy.
- Concomitant medication information and AEs to be collected if serious and considered to be study treatment-related.

Safety Follow-Up

Patients discontinuing treatment will be followed for the protocol required safety follow-up period, unless additional safety concerns warrant further follow-up:

- 30 days post treatment for LV and
- 90 days post treatment for pembrolizumab.

No additional follow-up is required after the safety follow-up period.

After disease progression or initiation of a new anticancer treatment, survival follow-up will be conducted, every 12 weeks (±2 weeks) starting from the last radiographic scan demonstrating disease progression or from initiation of the new anticancer treatment until completion of the safety follow-up period, death, or study closure, whichever comes first. Follow-up may be conducted with clinic visits or telephone calls. No further response assessments will be conducted.

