- I Blood glucose sample should be obtained before administration of study drugs or any glucose-containing fluid. Hold dose if blood glucose level is >250 mg/dL or >13.9 mmol/L, testing may be repeated on same day of dosing. If HbAlc or fasting glucose are elevated (HbAlc ≥6.5%, fasting glucose ≥126 mg/dL or ≥7.0 mmol/L) upon repeat testing, patient should receive glucose management prior to or within one week of starting study treatment.
- J Thyroid function tests include TSH, T3 or free T3, and free T4.
- K To be collected if serious and considered to be study treatment-related.
- L For patients who discontinue study treatment, perform every 6 weeks (±1 week) during the first year, then reduce frequency per institution's standard of care until progression or initiation of a new anticancer therapy unless otherwise stated.
- M For patients receiving >200 mg LV per infusion (weight >80 kg), prophylactic G-CSF administration is required and will be given to patients on the day after study treatment is given, with a visit window of Day 2-4. If pegfilgrastim is used, a one-time dose is recommended. If daily growth factor support is used, treat for at least 5-7 days or until the absolute neutrophil count is >1000/mm³ (< Grade 2). Hold dose if dosing criteria outlined in Section 5.2.3.5 are not met.
- N Timing of response assessments should be calculated from Cycle 1 Day 1.
- O Refer to the laboratory manual for information on collection, processing, storage, and shipment of sample.
- P Not required if conducted within 4 weeks prior to EOT.
- O Cycles 1-2 only
- R For Cycle 2 and beyond, may be performed up to 2 days prior to Day 1.
- S For Part A and Part B Cohort 1, laboratory assessments are to be performed locally and centrally. For Part B Cohort 2, laboratory assessments are to be performed locally and results are to be submitted to the central laboratory (with the exception of pregnancy testing); detailed in Section 7.5.3.
- T Follow-up will occur every 6 weeks (±1 weeks) 30 days post last treatment for patients on LV only and 90 days for those on pembrolizamab.

Page 106 of 152

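### Appendix G ends complete abstinence with safety follow-up (30 or 90 days), while Sections 4.1 and 4.2 use 6 months after the final dose

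*Protocol*

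**What the plan says.** **Appendix G (Protocol).** Complete abstinence is acceptable if it fits the patient's preferred lifestyle. It is defined as beginning at informed consent and "continuing throughout the study and until the end of the safety follow-up period". The appendix then lists the methods from which sexually active patients choose two, and gives no end date for that two-method rule.

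**Length of safety follow-up.** Section 6.6 sets 30 days after treatment for LV and "90 days post treatment for pembrolizumab", and allows a longer period if safety concerns warrant it. Appendix C footnote V gives "30 days post last treatment for patients on LV only and 90 days for those on pembrolizumab", and Appendix A footnote T gives the same periods.

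**Section 4.1, criterion 9b.** Patients of childbearing potential must agree not to try to conceive "from the time of enrollment until at least 6 months after the final dose of study drug". If heterosexually active, they must use two methods from Appendix G over the same period.

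**Section 4.1, criterion 10b.** Heterosexually active male patients must use two Appendix G methods, "continuing throughout the study and for at least 6 months after the final dose of study drug administration".

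**Section 4.2, criterion 27.** Patients are excluded if they are breastfeeding, pregnant or "planning to become pregnant from time of informed consent until 6 months after final dose of study drug administration".

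**Section 4.** "Eligibility criteria may not be waived by the investigator".

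**The concern.** Criteria 9b and 10b do not mention abstinence. They send the reader to Appendix G for acceptable methods, and Appendix G is the only place where abstinence is accepted and the only place where its duration is given. A site counselling an abstinent patient will use that definition, and it stops well before the period in the criteria that point to it.

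Section 1.4.2 reports that MMAE, the cytotoxic component of LV, given to pregnant rats raised resorptions and post-implantation loss and led to early delivery and loss of viable fetuses. It also reports damage to the spermatic epithelium with MMAE.

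Little scheduled contact would catch a misreading. The last planned pregnancy test is at the end-of-treatment visit (Section 7.5.5), normally 30 to 37 days after the last dose (Section 6.5). The Pregnancy Report Form requirement in Section 7.5.1.2 ends no later than completion of safety follow-up. After that, the patient has mainly the written guidance to go on, so its date should be right.

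**Working it through.** The plan states no figure for this gap, so there is none to reproduce. The check compares end dates and converts the difference to days.

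**Inputs**
- Required period: 6 months after the final dose (Section 4.1, criteria 9b and 10b; Section 4.2, criterion 27). Criteria 9b and 10b make it a minimum.
- Safety follow-up: 90 days on pembrolizumab, 30 days on LV only (Section 6.6; Appendix A footnote T; Appendix C footnote V).
- Conversion: 30.4375 days per month (SAP Section 5.4.1).

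**Step 1. Required period in days.** 6 × 30.4375 = 182.6 days after the final dose.

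**Step 2. Shortfall = required period − safety follow-up.**

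| Patient | Appendix G end | Shortfall in days | Shortfall in months |
|---|---|---|---|
| On pembrolizumab | day 90 | 182.6 − 90 = 92.6 | 92.6 / 30.4375 = 3.04 |
| On LV only | day 30 | 182.6 − 30 = 152.6 | 152.6 / 30.4375 = 5.01 |

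The Appendix G definition thus covers 90 / 182.6 = 49% of the required period for a patient on pembrolizumab and 30 / 182.6 = 16% for a patient on LV only.

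**Step 3. Patients who stopped pembrolizumab and continued LV.** All patients start on both drugs (Section 5.1), so an LV-only patient is one who has stopped pembrolizumab. The footnotes give this patient 30 days. Section 6.6 can instead be read as running each drug's period separately. If the last pembrolizumab dose came d days before the last LV dose, follow-up then ends at the later of day 30 and day 90 − d, counted from the last LV dose:
- d = 0: day 90, shortfall 92.6 days.
- d = 60 or more: day 30, shortfall 152.6 days.

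On that reading the LV-only shortfall lies between about 93 and 153 days.

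**Step 4. Whether the words about the whole study close the gap.** Appendix G also says abstinence continues throughout the study. Completing safety follow-up is a listed reason for leaving the study (Section 4.4.2), and Section 6.6 requires no further follow-up after it. Criterion 10b names the study period and then adds the 6 months, so the protocol does not treat the study period as already including them.

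**The case against.** The strongest reply is that the binding rule is intact. Under 9b the patient agrees not to try to conceive for at least 6 months whatever the method, and anyone who ends abstinence at day 90 and becomes heterosexually active falls under the two-method rule until month 6. The investigator cannot waive this. Appendix G is headed as guidance and is cited for methods, not for duration. All of this stands. It means the protection still exists in Section 4.1 and that the harm would come only through misreading. It does not make the Appendix G date correct.

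Four narrower points deserve an answer.
- *The sentence only separates complete from periodic abstinence.* It does make that distinction, but it also states an end date, and that date is the wrong one.
- *A patient who stops treatment without progression may stay on study past day 90.* The synopsis and the opening of Section 6.6 can be read that way. The later text of Section 6.6, together with Section 4.4.2, ends required follow-up with the safety period, so this cannot be relied on to reach month 6.
- *Exclusion 27 sets no contraception period.* Correct: it concerns being pregnant, breastfeeding or planning pregnancy. It still shows that 6 months is the reproductive-risk window used in Section 4.2.
- *The harm is not quantified.* Also correct. The rat data concern dosing during pregnancy, the documents give no risk estimate for day 90 to month 6, and the consent text was not available for this review.

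**Conclusion.** The Appendix G definition of complete abstinence conflicts with criteria 9b and 10b and with the window in exclusion 27, all in current Amendment 11 text. It is short by about 93 days (3.0 months) for patients on pembrolizumab, the usual case. For patients on LV only it is short by about 153 days (5.0 months) under the footnotes; that figure is an upper limit if each drug's follow-up is counted separately.

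These figures are counted from the final dose, use the SAP's days-per-month conversion and assume safety follow-up is not extended. The conflict is confined to this one sentence: the two-method rule has no shorter end date in Appendix G and still runs 6 months. The consequence is a risk of misreading in reproductive-safety guidance, with no effect on any endpoint or analysis. It should be corrected.

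**What to change.** In Appendix G, replace the end point in the abstinence definition with at least 6 months after the final dose of study drug, and add a cross-reference to Section 4.1.

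The cost is one phrase. It adds no visit, test, data item or analysis change, and no duty beyond what Section 4.1 already imposes. Extending the pregnancy reporting window in Section 7.5.1.2 to match is optional and is not needed to remove the conflict.
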